15. STUDY MEDICATION EXPOSURE AND COMPLIANCE

Exposure to study medication will be presented for the FAS.

Date of first dose is defined as the date of first non-zero study medication administration, which will be taken from the eCRF "HMPL-689 Treatment" form.

Date of last dose is defined as the date of last non-zero study medication on or prior to withdrawal from the study or cut-off date, which will be taken from the eCRF "HMPL-689 Treatment" form. For missing or partial end dates, see imputation rule in Section 7.10.

The extent of exposure to study medication will be presented for the following summaries:

Number of initiated cycles:
 Number of initiated cycles is the number of cycles in which the patient took any dose

Protocol Number: 2018-689-00US1 Page 29 of 43

of study medication.

Total duration of exposure (months):

Total duration of exposure (months)=
$$\left(\frac{\text{date of last dose - date of first dose+1}}{30.4375}\right)$$

- Number and percentage of patients with total duration of exposure
 - o < 6 months

 - o >=6 to < 12 months

 - >= 12 months
- Actual duration of study treatment (months):

Actual duration of study treatment is defined as the total number of months on the study medication during the treatment phase excluding the periods of dose break or dose interruptions.

Actual duration of study treatment (months) =
$$\left(\frac{\text{date of last dose - date of first dose - days with zero dose due to any cause +1}}{30.4375}\right)$$

Cumulative dose (mg):

Cumulative dose (mg) is defined as the sum of the total dosage that the patient actually received during an exposure period.

Dose intensity (mg/day):

Dose intensity
$$(mg/day) = \left(\frac{Cumulative dose (mg)}{total duration of exposure(days)}\right)$$

Relative dose intensity (%):

Relative dose intensity (%) =
$$\left(\frac{\text{dose intensity (mg/day)}}{\text{planned dose intensity (mg/day)}}\right) * 100$$

The planned dose intensity is the initial assigned dose intensity.

It will be summarized as a continuous variable and also categorized into groups as below:

- 0 < 50%
- o 50% <70%

- 0 70% < 90%
- o 90% <110%

- o >=110%

Details of study treatment administration and exposure endpoints will be included in patient listings.

16. EFFICACY OUTCOMES

The EAS is the primary analysis set for disease response efficacy endpoints including ORR, CBR, DoR and TTR. The FAS is regarded as primary analysis set for PFS. In the evaluation of the tumor response endpoints (ORR, TTR, CBR, DoR, and PFS), the investigator-

assessed data will be utilized for tumor assessment. Unless otherwise specified, all efficacy outcomes are to be summarized by dose level in stage 1 and by the malignancy type in stage 2. Tumor assessment will be conducted every 8 weeks (±7 days) for the first 24 weeks and then every 12 weeks (±7 days) thereafter.

Tumor assessment in different types of malignancies will be evaluated according to specified guidelines/criteria:

- CLL: the modified International Workshop on CLL guideline (Hallek 2008, Cheson 2012), see Appendix 5 of protocol amendment 5.
- LPL/WM: consensus of international workshops on WM (IWWM-7 consensus)
 (Dimopoulos 2014), see Appendix 6 of protocol amendment 5.
- Other lymphomas: Lugano Response Criteria for Hodgkin and Non-Hodgkin Lymphoma (Cheson 2014), see Appendix 7 of protocol amendment 5.

16.1. BEST OVERALL RESPONSE (BOR)

Best overall response is defined as the best response recorded from the start of treatment until disease progression or new anti-cancer therapy, whichever comes earlier.

Best overall response is determined from the sequence of responses assessed as below:

- For CLL guideline: Complete Response (CR), CR with incomplete bone marrow recovery (CRi), Partial Response (PR), Nodular Partial Response (nPR), Partial Response with Lymphocytosis (PR-L), Stable Disease (SD), Progressive Disease (PD), Not Evaluated (NE).
- For WM guideline: Complete Response (CR), Very Good Partial Response (VGPR), Partial Response (PR), Minor Response (MR), Stable Disease (SD), Progressive Disease (PD), Not Evaluated (NE).
- For Other Lymphomas guideline: Complete Response (CR), Partial Response (PR),
 Stable Disease (SD), Progressive Disease (PD), Not Evaluated (NE).

BOR will be assigned for each patient as the best response recorded from all responses recorded after study medication administration until disease progression or start of subsequent anti-tumor assessment, whichever comes earlier. For patients with multiple assessments on different dates for the same tumor assessment visit, the earliest date will be selected for PD, while the latest date will be selected for other responses.

Patients with BOR "NE" will be summarized by reason for having NE status. The following reasons will be used:

All post-baseline assessments have overall response NE

BOR data will be listed for all patients in EAS.

16.2. OBJECTIVE RESPONSE RATE (ORR)

Objective response rate (ORR) is defined as the proportion of patients who have BOR with CR, CRi, nPR or PR for CLL patients; proportion of patients who have BOR with CR, VGPR, PR or MR for WM patients; proportion of patients who have BOR with CR or PR for patients with disease type other than CLL and WM.

The definition of neo-OR is similar to classical OR except that partial response with lymphocytosis (PR-L) is also included for CLL.

The estimated ORR, neo-OR and 95% Clopper-Pearson confidence interval (CI) will be presented by dose level for Stage 1 and by the malignancy type stage 2. ORR data will be listed for all patients in EAS.

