CCI [REDACTED]

Amendment 5:

CCI

Statistical Analysis:

Data will be summarized by dose level, subtype of malignancy and for overall as appropriate. In Stage 2 of the protocol, each lymphoma subtype cohort will be analyzed independently and in aggregate. Continuous assessments will be summarized in descriptive statistics by the number of patients (n), mean, standard deviation, median, minimum and maximum. For categorical variables, descriptive statistics will include the number and percentage of patients for each category.

Safety Analysis:

Exposure to study drug will be summarized and listed.

Dose limiting toxicities will be listed. The incidence of TEAEs, SAEs, AEs of special interest, TEAEs leading to dose adjustment, or treatment discontinuation will be presented by Medical Dictionary for Regulatory Activities (MedDRA) System Organ Class (SOC) and preferred term, by relationship to study drug and by toxicity grade for each dose level. Shift of laboratory test results will be summarized according to the NCI CTCAE grade or normal ranges if not gradable. Descriptive statistics for vital signs and 12-ECG parameters will be presented by dose level and visit. Physical examination findings will be listed.

Pharmacokinetic Analysis:

Non-compartmental model and population model-based analyses will be performed for plasma concentration data. Individual and mean plasma concentrations of HMPL-689 versus time data will be tabulated and presented. Descriptive analysis (n, mean, standard deviation, minimum, median, maximum, geometric mean, and coefficient of variation [%CV]) for all of the relevant PK parameters of HMPL-689 will be presented. Individual and mean HMPL-689 concentrations will be plotted by dose level.

Efficacy Analysis:

The best percent change from baseline (%) in the target lesion, ORR, CBR and 95% CI based on Clopper-Pearson method will be presented by dose level for each type of malignancy. The PFS, TTR, and DoR will be estimated with Kaplan-Meier (KM) method if data permits, and the corresponding KM curve will be plotted for each type of malignancy.

Tumor assessment in different types of malignancies will be evaluated according to specified guidelines/criteria:

1. CLL: the modified International Workshop on CLL guideline
2. LPL/WM: consensus of international workshops on WM (IWWM-7 consensus)
3. Other lymphomas: Lugano Response Criteria for Hodgkin and NHL

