7.3.4 Efficacy Analysis

Efficacy endpoints will be summarized by dose level for each type of malignancy.

The best percent change from baseline (%) in the target lesion, ORR, CBR, and the corresponding 95% CI based on Clopper-Pearson method will be presented by dose level.

The PFS, TTR, and DoR will be summarized with Kaplan-Meier (KM) method if data permit, and the corresponding KM curve will be plotted.

ORR, CBR, PFS, TTR, and DoR data will be listed for all patients.

Tumor assessment in different types of malignancies will be evaluated according to specified guidelines/criteria:

- CLL: the modified International Workshop on CLL guideline ([Hallek 2008](#), [Cheson 2012](#)), see [Appendix 5](#).
- LPL/WM: consensus of international workshops on WM (IWWM-7 consensus) ([Dimopoulos 2014](#)), see [Appendix 6](#).
- Other lymphomas: Lugano Response Criteria for Hodgkin and NHL ([Cheson 2014](#)), see [Appendix 7](#).

In the evaluation of the tumor response endpoints (ORR, TTR, CBR, DoR, and PFS), the investigator-assessed data will be utilized for tumor assessment.

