3.2. SECONDARY OBJECTIVES

The secondary objectives are (for both stages):

- To assess preliminary efficacy of HMPL-689 in patients with relapsed, refractory, or resistant lymphoma overall and by lymphoma sub-types as assessed by investigator.
- To characterize PK parameters of HMPL-689 in patients with relapsed, refractory, or resistant lymphoma at both dose escalation and dose expansion stages.
- To evaluate the effect of HMPL-689 on cardiac repolarization, as detected by changes in electrocardiogram (ECG) QTc intervals.

Table 1 Objectives and Corresponding Endpoints

Tier Objectives and Corresponding Endpoints Endpoints		
Primary – Dose Escalation	•	 Incidence of DLTs Safety (including but not limited to TEAEs, treatment-related adverse events [TRAEs], SAEs, treatment-related SAEs [TRSAEs], and lab abnormalities)
Primary – Dose Expansion	To further evaluate safety and tolerability of HMPL-689 at MTD in patients with relapsed, refractory, or resistant lymphoma	Safety, including TEAEs and TRAEs
	To assess preliminary efficacy of HMPL689 in patients with relapsed, refractory, or resistant lymphoma overall and by lymphoma sub-types as assessed by investigator	 ORR TTR DoR CBR PFS
Secondary	To characterize PK parameters of HMPL-689 in patients with relapsed, refractory, or resistant lymphoma at both dose escalation and dose expansion stages	Concentration-time profiles and PK parameters after single dose and at steady state
	To evaluate the effect of HMPL- 689 on cardiac repolarization, as detected by changes in electrocardiogram (ECG) QTc intervals	QTc interval and HMPL-689 concentration

Abbreviations: CBR = clinical benefit rate; DLT = dose-limiting toxicity; DoR = duration of response; MTD = maximum tolerated dose; ORR = objective response rate; PD = progressive disease; PFS = progression-free survival; PK = pharmacokinetic; RP2D = recommended phase 2 dose; SAE = serious adverse event; TEAE = treatment-emergent adverse event; TRAE = treatment-related adverse event; TRSAE = treatment-related serious adverse event; TTR = time to response.

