8. OUTPUT PRESENTATIONS

Summary results will be presented separately by Stage 1 and Stage 2.

Efficacy analysis: For Stage 1, summary will be by dose level. For Stage 2, summary will be by type of malignancies.

Analysis other than efficacy: For Stage 1, summary will be by dose level and total. For Stage 2, summary will be by type of malignancies and total.

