16.4. CLINICAL BENEFIT RATE (CBR)

CBR is defined as the proportion of patients who have BOR with stable disease (SD) or better

The clinical benefit for each type of malignancy is defined as following:

- CLL: BOR with CR, CRi, nPR, PR, PR-L or SD
- WM: BOR, with CR, VGPR, PR, MR or SD
- Other types of disease: CR, PR or SD

The estimated CBR and the corresponding 95% exact CI calculated using the Clopper-Pearson method will be presented by dose level in Stage 1 and type of the malignancy for stage 2.

CBR data will be listed for all patients in EAS.

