- From Day 162 (week 24) onwards (when the scheduling changes to 12-weekly assessments), two missing consecutive assessments equates to 182 days (2*12 weeks + 7 days for an early assessment + 7 days for a late assessment) since last evaluable tumor assessment.

[b] for patients who receive new anti-cancer therapy, the following rules will apply:

If the start date of new anti-cancer therapy is partial or missing, the imputation rules refer to section 7.10.

If an assessment occurs on the same day as the start of new anti-cancer therapy, the assessment will be used as it will be assumed the assessment occurred prior to the administration of new anti-cancer therapy).

The median and quartiles for PFS and the PFS rates at 6 months, 12 months, together with their two-sided 95% confidence intervals will be estimated for each dose level (Stage 1) and malignancy type (Stage2) using the Kaplan-Meier method. The 95% CI for the median will be calculated from a log-log transformation based on the method by Brookmeyer and Crowley (1982).

Kaplan-Meier curves will be plotted. In case the number of responses in each group is very small, PFS may be listed only.

PFS follow-up time will be summarized by reversed Kaplan-Meier method (i.e. using different censoring rule which reverses censoring indicator of PFS, i.e. patients who progressed or died in PFS analysis will be censored at the date of progression or death, patients who are censored in PFS analysis will be assigned indicator of "event" with the same duration for PFS) to calculate median, first and third quartiles and 95% CIs.

Frequency and percentage for each type of event (PD or death) and censoring reasons will be presented as categories.

The PFS time or censoring time and the reasons for censoring will also be presented in a patient listing for FAS.

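### The SAP summarises Stage 1 efficacy by dose level only, with no total, so the sub-type and overall parts of the efficacy objective get no Stage 1 summary

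*SAP*

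**What the plan says.** **Protocol.** Section 7.3.4 opens: "Efficacy endpoints will be summarized by dose level for each type of malignancy". The synopsis repeats this for response, stating that ORR, CBR and the "95% CI based on Clopper-Pearson method will be presented by dose level for each type of malignancy", and it asks for Kaplan-Meier curves of PFS, TTR and DoR for each type. Section 7.3 is looser: it names dose level, sub-type and overall, but only as appropriate, and leaves detail to the SAP.

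**SAP, objective.** Section 3.2 introduces its list with the words "The secondary objectives are (for both stages". The first item is preliminary efficacy, overall and by lymphoma sub-type.

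**SAP, analysis.** The general rule in section 16 is that "all efficacy outcomes are to be summarized by dose level in stage 1 and by the malignancy type in stage 2". Section 8 sets the same layout: "Efficacy analysis: For Stage 1, summary will be by dose level. For Stage 2, summary will be by type of malignancies". It provides a total column only for outputs other than efficacy. The endpoint sections agree. ORR "will be presented by dose level for Stage 1 and by the malignancy type stage 2". CBR "will be presented by dose level in Stage 1 and type of the malignancy for stage 2". PFS quantiles and rates "will be estimated for each dose level (Stage 1) and malignancy type (Stage2) using the Kaplan-Meier method". CR rate, DoR and TTR (16.3, 16.6, 16.7) are laid out likewise. Section 7.6 marks subgroups as not applicable. The SAP gives no reason for departing from the protocol's layout.

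**The concern.** SAP 3.2 promises a sub-type answer and an overall answer for both stages. The table plan delivers neither for Stage 1. The sub-type breakdown appears only in Stage 2, and there is no Stage 1 efficacy total.

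The one summary that remains, by dose level, is also hard to read alone. Protocol 5.1.1 admits seven disease groups. Protocol 5.3 assigns Stage 1 patients to dose levels sequentially and uses disease sub-type for allocation only in expansion, so nothing balances type across doses. Under SAP 16.2 a minor response counts towards ORR in WM, while PR-L in CLL counts only towards neo-OR. A Stage 1 ORR for one dose level is therefore an average over whichever diseases were enrolled there. A difference between two dose levels can come from the mix.

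**Working it through.** No sample size, power or error rate in the plan bears on this point, and the planned Stage 1 number is redacted, so there is no design figure to reproduce. The check has three parts.

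**1. Objective against planned Stage 1 output**

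| Element | Specified in | Stage 1 summary in SAP |
|---|---|---|
| Efficacy by dose level | Protocol 7.3.4, synopsis | Yes (8, 16 to 16.7) |
| Efficacy by sub-type | SAP 3.2; Protocol 7.3.4, synopsis | None |
| Efficacy overall | SAP 3.2 | None (8 gives a total only for non-efficacy outputs) |
| Tumour type by dose level | – | Yes (11 with 8) |
| Patient-level response, PFS and diagnosis | – | Listings (16.1 to 16.7, 11) |

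**2. How far case mix alone can move a by-dose figure**

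Protocol 2.3 gives rates at a single dose in the China study: FL 14/18 = 77.8% and MZL 6/12 = 50.0%. Take these as true rates and assume two dose groups of six patients with no dose effect.

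- *Moderate imbalance, 4 FL + 2 MZL against 2 FL + 4 MZL.* Expected ORR is (4 × 0.778 + 2 × 0.500)/6 = 68.5% against (2 × 0.778 + 4 × 0.500)/6 = 59.3%, a gap of 9.3 points. Summing exact binomial probabilities, the first group has at least 2 more responders with probability 0.28. For two groups each of 3 FL + 3 MZL the probability is 0.17.
- *Extreme, all FL against all MZL.* The gap is 77.8 − 50.0 = 27.8 points. The same probability is 0.55, against 0.14 if both groups are all FL.

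The inputs are imprecise: the exact 95% intervals are 52% to 94% (FL) and 21% to 79% (MZL), and Fisher's exact test of the two rates gives p = 0.14.

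For PFS, Protocol 2.4 cites idelalisib medians of 11 months in indolent NHL and 3.7 months in MCL. Under an assumed exponential distribution, 6-month PFS = 2^(−6/median): 2^(−6/11) = 68.5% and 2^(−6/3.7) = 32.5%. SAP 16.5 reports 6-month PFS by dose level.

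**3. What Stage 1 could support**

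The maximum in Protocol 7.1.1 is k × (d + 1). With k = 3 (the stated minimum cohort) and d = 10 dose levels, it is 3 × 11 = 33; counting dose level −1 as well, it is 3 × 12 = 36. With seven disease groups and an even spread:

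- dose by type: 10 × 7 = 70 cells, 33/70 ≈ 0.5 patients per cell;
- type pooled over doses: 33/7 = 4.7 to 36/7 = 5.1 patients per type.

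The exact 95% interval for 1 responder of 1 patient is 2.5% to 100%. Intervals within dose-by-type cells would say nothing; counts by type are feasible.

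**The case against.** The strongest reply is that the protocol's wording is mixed and that its literal layout is useless. Protocol 7.3 qualifies the breakdown, the ORR and CBR sentence in 7.3.4 names dose level alone, and the synopsis places the cohort-by-cohort sub-type analysis in Stage 2. A 70-cell table for some 33 patients would be nearly empty. The small-cell argument stands and shapes the fix. The latitude argument does not settle the matter: the lead sentence of 7.3.4 and the synopsis are explicit, SAP 3.2 applies the objective to both stages, and the SAP states no reason.

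Three other replies limit the consequence, and they stand.

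- *RP2D.* A reader might infer that pooled tables distorted the dose choice, because Protocol 4.1.1.7 lets preliminary efficacy inform it. The documents do not support that. Expansion patients are dosed at the RP2D (Protocol 4.1.2), Amendment 5 halted further enrolment, and the final analysis follows end of study and database lock (SAP 5). The dose choice precedes these tables, and efficacy was an optional input to it.
- *Lost information.* A reader might infer that Stage 1 sub-type results cannot be recovered. They can be rebuilt from the response and diagnosis listings, and SAP 11 with SAP 8 already tabulates tumour type by dose level. What is missing is the summary.
- *Size.* The 28-point gap is an extreme that nothing in the documents suggests occurred. It is also tempting to add the other patients of the China study: 31 − 14 − 6 − 4 = 7 responders among 60 − 18 − 12 − 5 = 25. That study included DLBCL, which is not eligible here, so this remainder is not used.

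Pooling over disease-specific response criteria is not itself an error, since an overall result requires it. The difficulty is pooling with no accompanying breakdown.

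**Conclusion.** The inconsistency is real. For Stage 1 the SAP omits the by-type and overall efficacy summaries that its own objective calls for, and drops the protocol's breakdown by type without explanation. By-dose ORR and PFS then mix diseases of different prognosis and response definition.

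The consequence is limited to descriptive reading. No dose comparison is tested, so no error rate is affected, and the RP2D choice is not in question. Case mix alone moves expected ORR by about 9 points in a moderately unbalanced pair of groups and 28 at the extreme. Both figures rest on assumed groups of six and on imprecise rates from another study; the actual Stage 1 mix is unknown. The change should be made because it closes a gap between objective and output at little cost.

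**What to change.** In SAP 8 and 16.2 to 16.7, add for Stage 1:

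- an overall column in the efficacy tables;
- tables of BOR, ORR and neo-OR, CR rate, CBR, PFS, DoR and TTR by malignancy type, pooled over dose levels, with time-to-event endpoints listed only where numbers are very small (SAP 16.5 already allows this for PFS);
- responders/n by dose level within type, as counts without confidence intervals;
- a cross-reference from the by-dose efficacy tables to the tumour-type table under SAP 11, which already shows the mix.

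State in the SAP that the dose-within-type display is reduced to counts and why, so that the difference from Protocol 7.3.4 is documented.

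The cost is SAP wording and a re-run of existing table programs, with no new data and no change to conduct. The drawback is small cells: about 5 patients per type if Stage 1 has roughly 33 patients evenly spread, which is an assumption because the planned number is redacted.

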16.3. COMPLETE RESPONSE RATE (CR RATE)

CR rate is defined as the proportion of patients who have BOR with CR or CRi for CLL patients, and CR only for other patients.

The estimated CR rate and 95% Clopper-Pearson confidence interval (CI) will be presented by dose level for Stage 1 and by the malignancy type for stage 2. CR rate data will be listed for all patients in EAS.

16.4. CLINICAL BENEFIT RATE (CBR)

CBR is defined as the proportion of patients who have BOR with stable disease (SD) or better

The clinical benefit for each type of malignancy is defined as following:

- CLL: BOR with CR, CRi, nPR, PR, PR-L or SD
- WM: BOR, with CR, VGPR, PR, MR or SD
- Other types of disease: CR, PR or SD

The estimated CBR and the corresponding 95% exact CI calculated using the Clopper-Pearson method will be presented by dose level in Stage 1 and type of the malignancy for stage 2.

CBR data will be listed for all patients in EAS.

16.5. PROGRESSIVE-FREE SURVIVAL (PFS)

PFS is defined as the time (in months) from the date of first study medication to the earliest date of disease progression or death of any cause, whichever occurs first.

Protocol Number: 2018-689-00US1 Page 32 of 43

Progression-free survival (PFS) (months) = (<date of progression or death or censoring > - <date of first dose of study medication> + 1)/30.4375.

A patient is deemed to be censored, according to the rules specified in Table 4 below:

Table 2 Progression-Free Survival Censoring Rule

-	Τ	D (CD :		E 4/6
#	Situation	Date of Progression	Outcome	Event/Censor reason
		or Censoring		
1	Death (without previously	Date of death	Event	Death
	documented progressive disease			
	[PD]) within two evaluable			
	tumor assessments[a] from last			
	evaluable tumor assessment or			
	first dose (if no post-baseline			
	tumor assessment)			
2	Death (without previously	Date of last evaluable	Censored	Death after two or more
	documented PD) after two or	tumor assessment or		consecutive missed or
	more consecutive missed/non-	date of first dose (if no		NE tumor assessments
	evaluable tumor assessments[a]	post-baseline tumor		
	from last evaluable tumor	assessment)		
	assessment or first dose (if no			
	post-baseline tumor assessment)			
3	Progression within two	Date of progression	Event	Disease Progression
	evaluable tumor assessments[a]			
	from last evaluable tumor			
	assessment or first dose (if no			
	post-baseline tumor assessment			
 	before PD)	D . Cl . 1 11		
4	Progression after two or more	Date of last evaluable	Censored	Progression after two or
	consecutive missed/non-	tumor assessment or		more consecutive
	evaluable tumor assessments ^[a]	date of first dose (if no		missed or NE tumor
	from last evaluable tumor	post-baseline tumor		assessments
	assessment or first dose (if no	assessment before PD)		
	post-baseline tumor assessment			
5	before PD)	Date of last evaluable	Censored	Deagrassian - A
3	Progression after new anti-		Censorea	Progression after new
	cancer treatment	tumor assessment before new anti-cancer		anti-cancer therapy
		treatment or date of		
		first dose (if no post-		
		baseline tumor		
		assessment before new		
		anti-cancer)		
6	No baseline tumor evaluable	Date of first dose	Censored	No baseline assessment
١	assessment and alive	Date of first dose	Censored	No baseine assessment
1	LASSESSIFICITE ALICE ALIVE		- 1	27 (1 1)
7		Date of first dose	Cencored	No noct-baceline
7	No post-baseline tumor	Date of first dose	Censored	No post-baseline
	No post-baseline tumor evaluable assessment and alive			assessment
7 8	No post-baseline tumor evaluable assessment and alive New anti-cancer treatment	Date of last evaluable	Censored	assessment Initiation of new anti-
	No post-baseline tumor evaluable assessment and alive			assessment

		treatment or date of first dose (if no post- baseline tumor assessment before new anti-cancer)		
9	No disease progression or death Note: use last tumor assessment before two or more consecutive missed/non-evaluable tumor assessments (if exists)	Date of last evaluable	Censored	Progression free at time of analysis: the patient is known to be alive without any progression happened at the data cut- off date

Note: Only for tumor assessments and death date before cutoff date.

[a] time period that identifies two consecutive missed/non-evaluable tumor assessments is calculated as 2*(the planned duration between assessments + protocol allowed visit window) from the last evaluable tumor assessment or (2*the planned duration between assessments + 1*protocol allowed visit window) from date of first dose (if no post-baseline evaluable tumor assessment).

According to protocol, tumor assessment will be conducted every 8 weeks for the first 24 weeks and every 12 weeks thereafter (±7 days). Given the schedules visit assessment scheme, the definition of two missed consecutive tumor assessment visit may vary, please refer to following rule:

- If the last evaluable tumor assessment before PD/death is on or before Day 105 (week 15, which is 8 weeks before week 24, and allowing for 7 days for early visit, hence 7*16 weeks 7 days for a late visit =Day 105), then two consecutive assessments equates to 126 days since last evaluable tumor assessment, allowing for early and late visits (2*8 weeks + 7 days for an early assessment + 7 days for a late assessment), or 119 days since date of first dose, allowing for late visit (2*8 weeks + 7 days for a late assessment).
- If the two missed assessments occur over the period when the scheduled frequency of tumor assessments change from 8-weekly to 12-weekly, which means last evaluable tumor assessment is from week 16 to 23 (Day 106 to Day 161), then two consecutive assessments equates to 154 days (7*8 weeks + 7*12 weeks + 7 days for an early assessment + 7 days for a late assessment) since last evaluable tumor assessment.
- From Day 162 (week 24) onwards (when the scheduling changes to 12-weekly assessments), two missing consecutive assessments equates to 182 days (2*12 weeks + 7 days for an early assessment + 7 days for a late assessment) since last evaluable tumor assessment.

[b] for patients who receive new anti-cancer therapy, the following rules will apply:

If the start date of new anti-cancer therapy is partial or missing, the imputation rules refer to section 7.10.

If an assessment occurs on the same day as the start of new anti-cancer therapy, the assessment will be used as it will be assumed the assessment occurred prior to the administration of new anti-cancer therapy).

The median and quartiles for PFS and the PFS rates at 6 months, 12 months, together with their two-sided 95% confidence intervals will be estimated for each dose level (Stage 1) and malignancy type (Stage2) using the Kaplan-Meier method. The 95% CI for the median will be calculated from a log-log transformation based on the method by Brookmeyer and Crowley (1982).

Kaplan-Meier curves will be plotted. In case the number of responses in each group is very small, PFS may be listed only.

PFS follow-up time will be summarized by reversed Kaplan-Meier method (i.e. using different censoring rule which reverses censoring indicator of PFS, i.e. patients who progressed or died in PFS analysis will be censored at the date of progression or death, patients who are censored in PFS analysis will be assigned indicator of "event" with the same duration for PFS) to calculate median, first and third quartiles and 95% CIs.

Frequency and percentage for each type of event (PD or death) and censoring reasons will be presented as categories.

The PFS time or censoring time and the reasons for censoring will also be presented in a patient listing for FAS.

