6.2. FULL ANALYSIS SET (FAS)

The full analysis set (FAS) is defined as all patients who receive at least one dose of HMPL-689. The FAS will be used for analysis of safety data and efficacy endpoint PFS.

Patients will be analyzed by their actual dose initially received. If patients had their dose reduced during the study, all data will be summarized/analyzed based on the initial dose of study treatment received. However, some listings such as AE listings may give the actual dose to the patient received at the time of the AE (e.g. reduced dose, interruption etc.).

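### SAP 16.5 lets the Kaplan-Meier PFS summary of a group be replaced by a listing because of few responses, a count that does not determine whether PFS can be estimated

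*SAP*

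**What the plan says.** SAP 16.5 defines PFS as running "from the date of first study medication to the earliest date of disease progression or death of any cause". SAP 6.2 fixes the population: "The FAS will be used for analysis of safety data and efficacy endpoint PFS". The FAS is every patient with at least one dose.

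The planned outputs in SAP 16.5 are "The median and quartiles for PFS and the PFS rates at 6 months, 12 months, together with their two-sided 95% confidence intervals", which "will be estimated for each dose level (Stage 1) and malignancy type (Stage2) using the Kaplan-Meier method", plus the curves. Directly after the sentence on curves comes the exception: "In case the number of responses in each group is very small, PFS may be listed only". No cut-off is given, and the verb makes the step optional.

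Two further outputs are planned in the same section: "Frequency and percentage for each type of event (PD or death) and censoring reasons will be presented as categories", and "The PFS time or censoring time and the reasons for censoring will also be presented in a patient listing for FAS".

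SAP 16.6 restricts DoR to responders but has no list-only exception. Protocol 7.3.4 and the synopsis make Kaplan-Meier for PFS, TTR and DoR conditional only on the data permitting it, without mention of responses.

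**The concern.** Whether a Kaplan-Meier estimate is informative depends on how many patients are followed and how many progress or die. Response enters neither the PFS event nor the PFS denominator. A group with few responders may well have many PFS events, because non-responders tend to progress early.

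The exception therefore ties the display of one efficacy endpoint to the result of another in the same patients. It has no threshold and is discretionary. The study is open-label with investigator-assessed response, and SAP 5 allows accrued cohort data to be analysed for internal decisions, so the choice can be made with the results known. PFS is a named secondary endpoint, to be assessed overall and by lymphoma sub-type. A report could then show PFS estimates with intervals for some sub-types and only a listing for others, with response count deciding which.

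**Working it through.** The plan states no figure for this rule, so there is nothing to reproduce. The check has three parts.

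**1. Which count limits which endpoint**

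| | PFS (SAP 16.5) | DoR (SAP 16.6) |
|---|---|---|
| Patients analysed | all FAS patients | responders only |
| Event | progression or death | progression or death |
| Do responses limit the analysis? | no | yes |
| List-only rule based on responses? | yes | no |

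The rule sits with the endpoint that does not need it and is absent from the one that might.

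**2. How often the option would be open**

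Assumptions: the cut-off is 2 or fewer responses (the SAP gives none), and a group has 20 patients (Stage 2 cohort sizes are redacted). With X responses among n patients at true response rate p:

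P(X ≤ 2) = (1−p)^n + n·p·(1−p)^(n−1) + [n(n−1)/2]·p²·(1−p)^(n−2)

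For n = 20:

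- p = 10%: 0.1216 + 0.2702 + 0.2852 = 0.677
- p = 20%: 0.0115 + 0.0576 + 0.1369 = 0.206
- p = 30%: 0.0008 + 0.0068 + 0.0278 = 0.035
- p = 50%: (1 + 20 + 190)/2^20 = 0.0002

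The cut-off matters. For n = 20 and p = 10%, dropping the last term (cut-off of 1) gives 0.392. Adding P(X = 3) = 0.190 (cut-off of 3) gives 0.867.

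Group size matters too, at a cut-off of 2:

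| n | p = 10% | p = 20% | p = 30% | p = 50% |
|---|---|---|---|---|
| 10 | 0.930 | 0.678 | 0.383 | 0.055 |
| 20 | 0.677 | 0.206 | 0.035 | 0.0002 |
| 30 | 0.411 | 0.044 | 0.002 | about 0 |

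The trigger is a count, not a rate. SAP 4.2 sets a minimum cohort of 3 in Stage 1. At p = 77.8% (the follicular lymphoma response rate for this drug in Protocol 2.3), P(X ≤ 2) = 1 − 0.778³ = 0.53.

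**3. Whether such a group lacks PFS data**

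Assume exponential PFS with a median of 3.7 months, the Protocol 2.4 figure for idelalisib in mantle cell lymphoma, used here as a stand-in for a poorly responding group. Expected events = n × (1 − 0.5^(t/3.7)). For n = 20:

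- t = 6 months: 20 × 0.675 = 13.5
- t = 12 months: 20 × 0.894 = 17.9
- t = 18 months: 20 × 0.966 = 19.3

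The Kaplan-Meier median was also simulated for n = 20, with 4,000 runs and censoring uniform over 6 to 18 months. It could be estimated in 100% of runs at a median of 2 or 3.7 months, 99.9% at 5.5 months and 82% at 11 months.

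These event counts lean high. Under Amendment 5, patients who stop treatment for reasons other than progression also leave the study (Protocol 5.8.2), which adds earlier censoring than the illustration allows for.

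**The case against.** The other side has good points, and several narrow the finding.

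- **The data do not disappear.** The FAS listing carries every PFS and censoring time, and an event and censoring table is planned. ORR and CBR with exact intervals are reported for every group. This stands: low activity could not be hidden. Still, a listing is not an estimate with an interval when other groups show theirs.
- **It may only be a clumsy small-group rule.** A reader might infer that PFS is withheld exactly where the drug works least. The documents do not support that. The trigger is a count, so it also catches small groups whatever their activity. The link to low activity holds only between groups of similar size.
- **No estimate is biased.** A reader might infer that PFS across sub-types will look better than it is. Leaving out one group's curve does not alter another group's estimate. The risk is selective display.
- **It is not the only condition.** The protocol separately requires that the data permit Kaplan-Meier. True, but that concerns adequacy of data and does not call for a response trigger.
- **The wording may be a slip.** *Responses* may be meant as *events*, the text may belong under DoR, or the phrase about each group may mean all groups together. Any of these is possible, and under each the sentence still needs correcting.
- **The response rates may be unrealistic.** Protocol 2.3 reports 77.8% in follicular, 50.0% in marginal zone and 80.0% in mantle cell lymphoma for this drug, and Protocol 2.4 cites about 30% to 50% for the class in peripheral T-cell lymphoma. At 30% to 50% and n = 20, the probability is 3.5% or less. At n = 10 and 30% it is still 38%.

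**Conclusion.** The point holds in a limited form. The trigger in SAP 16.5 names a quantity that does not determine whether PFS can be estimated, leaves it undefined, and makes the step optional. The sponsor may therefore omit the Kaplan-Meier summary of a secondary endpoint for a low-response group with ample PFS events. The documents do not support reading this as hiding PFS data or as inflating any estimate.

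The probabilities are illustrative. They rest on an assumed cut-off of 2 and assumed group sizes, and they measure how often the option would be open, not how often it would be used. The logical fault does not depend on them. In a descriptive phase 1 study with no PFS test or decision rule in the available text, this should be corrected, but it does not undermine the trial.

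**What to change.** Delete the response-based sentence from SAP 16.5 and put in its place a rule of this kind: *PFS is listed only for groups with fewer than N FAS patients; for every other group the Kaplan-Meier median, quartiles, 6- and 12-month rates and curve are presented whatever the number of responses, with values shown as not reached or not estimable where needed.* The sponsor sets N before database lock and applies it to all groups.

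The number of FAS patients is the cleanest trigger because it depends on no outcome. A minimum number at risk would also cut the link to response, but that number falls as patients progress, so it is better used to mark a landmark rate as not estimable than to drop a group.

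If a response-based rule is wanted, state it with a cut-off in SAP 16.6 for DoR. The cost is one SAP edit, a few more table rows and curves, and some wide intervals on display.
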